6.2. Overall Study Design

The overall sequence of study events is shown in Figure 1. During Screening, patients will have their SOC vasopressors titrated to an age-, size-, and disease-appropriate MAP (Appendix A, Dellinger 2013) at the discretion of the Investigator. A minimum titration period of 2 hours, and a maximum of 48 hours, is required. The Screening MAP is calculated as the average of at least two once-hourly MAP readings during SOC vasopressor titration, and within 24 hours prior to LJPC-501 treatment initiation.

In the 15 minutes prior to initiation of LJPC-501 dosing, a baseline MAP will be documented. The Baseline MAP is the average of 3 recorded MAP values documented within 15 minutes prior to initiation of LJPC-501 (ie, at approximately -15 minutes, -5 minutes, and 0 minutes or just prior to initiation of LJPC-501 administration).

After obtaining informed consent from the patients' parent(s) or legal guardian(s), assent from the patients (per institutional requirements, as age appropriate, if possible), and confirmation of eligibility, patients will begin LJPC-501 treatment at a dose rate of 5 ng/kg/min. The goal at Hour 2 of LJPC-501 administration is to increase the Baseline MAP by 25% or to decrease the

sum NED by 25%. The LJPC-501 dose will be titrated during this period according to the guidelines in Section 8.3, to achieve a MAP above baseline, but less than 90 mmHg. Throughout treatment, the LJPC-501 dose rate may be increased to a maximum rate of 40 ng/kg/min, and decreased to a minimum of 1.25 ng/kg/min. If MAP exceeds 90 mmHg, SOC vasopressors should be down-titrated first, then LJPC-501 should be down-titrated if MAP remains \geq 90 mmHg. Any decision to increase the dose rate above 40 ng/kg/min must be made in consultation with Sponsor. With Sponsor approval, the dose rate may be increased to a maximum of 80 ng/kg/min. Unless adjustment is required for safety reasons, SOC vasopressor dosing should be decreased, but not increased, during the first 2 hours of LJPC-501 treatment (ie, up to the Hour 2 time point). MAP should not be allowed to decrease below baseline.

[figure not shown]
A schedule of study procedures is shown in Table 4. Patients will be monitored for hemodynamic vital signs (MAP, HR) at Screening and at approximately -15, -5 and 0 minutes (or just prior to initiation of LJPC-501 dosing) to establish the Baseline MAP value. MAP should be assessed once every 5 minutes during the first 15 minutes of LJPC-501 treatment, then once every 15 minutes up to the Hour 2 time point and at least once hourly thereafter through the duration of LJPC-501 administration (at minimum 24 hours). Additionally, MAP should be assessed just prior to every dose titration. If LJPC-501 administration is continued for longer than 24 hours, MAP should be assessed hourly and just prior to any dose adjustment until LJPC-501 is discontinued.

[figure not shown]
Treatment with LJPC-501 will continue to Hour 24, with the goal of maintaining age-, size-, and disease-appropriate MAP (Appendix A, Dellinger 2013), while reducing the reliance on SOC vasopressors. Down-titration of SOC vasopressors should be done according to individual institutional protocols and the Investigator's discretion.

After 24 hours, LJPC-501 treatment may be stopped or continued up to 7 days (168 hours) at the Investigator's discretion. It is recommended that the Investigator check in with the Sponsor's contact to continue treatment for more than 24 hours. If the Investigator determines that it is necessary to discontinue LJPC-501 prior to Hour 24, the Sponsor should also be consulted prior to discontinuation. To stop treatment, LJPC-501 will be titrated off by decreasing the dose at the Investigator's discretion and according to guidelines in Section 8.3.2. After Hour 24, if LJPC-501 treatment has been stopped for 3 hours or less, the Investigator may reinitiate treatment after consultation with Sponsor; if treatment has been stopped for more than 3 hours it may not be reinitiated. All patients will be followed for a minimum of 7 days, or for 72 hours (3 days) \pm 6 hours following discontinuation of LJPC-501, whichever is later, before end-of-study (EOS) assessments.

All components of the PELOD, PRISM, and PIM2 scores will be collected during Screening (no more than 6 hours prior to the initiation of LJPC-501 dosing) and at Hour 24. If possible, blood samples to determine the levels of endogenous angiotensin II and its precursor, angiotensin I, will be obtained at Screening prior to LJPC-501 administration. Safety will be addressed by assessing AEs, BP, HR, and routine clinical safety laboratory testing including blood chemistry, hematology, and urine output. A follow-up phone call and/or chart review will occur at approximately 28 days following initiation of LJPC-501 for safety assessments.

This study will be overseen by an independent external Data Safety Monitoring Board (DSMB).

Abbreviations: EOS=end of study; SOC=standard of care

6.3. Treatment Assignment

All patients will receive LJPC-501 in this single-arm, open-label study.

6.4. Number of Subjects

The study will include 10 to 30 pediatric patients.

6.5. Dose Rationale

Patients will receive an initial LJPC-501 dose rate of 5 ng/kg/min. Throughout treatment, the LJPC-501 dose rate may be increased to a maximum rate of 40 ng/kg/min, and decreased to a minimum of 1.25 ng/kg/min, to achieve an age-, size- and disease-appropriate MAP (Appendix A, Dellinger 2013). Any decision to increase the dose rate above 40 ng/kg/min must be made in consultation with Sponsor. With Sponsor approval, the dose rate may be increased to a maximum of 80 ng/kg/min.

In the recently completed double-blind, placebo-controlled Phase 3 clinical study, LJPC-501 was found to be efficacious in patients ≥ 18 years old with hypotension (Section 4.5). The starting dose was 20 ng/kg/min, and the dose rate range allowed per protocol was 2.5 ng/kg/min to 200 ng/kg/min during the first 3 hours 15 minutes of treatment. Thereafter, the allowed dose rate range was 2.5 to 40 ng/kg/min. A minimum dose rate of 1.25 ng/kg/min was allowed if MAP remained ≥ 70 mmHg without vasopressin and with NED as low as 0.03 µg/kg/min. Per protocol, the dose was titrated based on the observed MAP. By 30 minutes, 67% of patients in the LJPC-501 group were receiving doses below 20 ng/kg/min, including 48.4% with doses of 5 ng/kg/min or less and 23.9% with doses of 2.5 ng/kg/min or less, demonstrating that doses below 20 ng/kg/min were effective.

6.6. Dose Adjustment Criteria

LJPC-501 dose may be titrated to achieve an age-, size-, and disease-appropriate MAP, which should remain above baseline, but less than 90 mmHg. Throughout treatment, LJPC-501 dose may be decreased to a minimum of 1.25 ng/kg/min and increased to a maximum rate of 40 ng/kg/min. If MAP exceeds 90 mmHg, SOC vasopressors should be down-titrated first, then LJPC-501 should be down-titrated if MAP remains \geq 90 mmHg. Any decision to increase the dose rate above 40 ng/kg/min must be made in consultation with Sponsor. With Sponsor approval, the dose rate may be increased to a maximum of 80 ng/kg/min. Dose titration guidelines are provided in Section 8.3.2.

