- 7. Patients with a clinical suspicion of cardiogenic shock
- 8. Patients who have a history of asthma or are currently experiencing bronchospasm requiring the use of inhaled bronchodilators and who are not mechanically ventilated.
- 9. Patients with acute mesenteric ischemia or a history of mesenteric ischemia.
- Patients with active bleeding AND an anticipated need of multiple transfusions (within 48 hours of Screening).
- 11. Patients with active bleeding AND hemoglobin < 7 g/dL or any other condition that would contraindicate serial blood sampling.
- 12. Patients requiring more than 5 mg/kg daily of hydrocortisone or equivalent glucocorticoid medication as a standing dose.
- 13. Patients with an expected lifespan of < 12 hours or withdrawal of life support within 24 hours of Screening.
- 14. Patients with a known allergy to mannitol.
- 15. Patients who are currently receiving an investigational drug (active or placebo) as part of another clinical trial.

16. Patients of childbearing potential who are known to be pregnant at the time of Screening.

Investigational product, dosage and mode of administration:

LJPC-501 for intravenous (IV) infusion: 2.5 mg per mL

Patients will begin LJPC-501 treatment by IV infusion at a dose rate of 5 ng/kg/min. The dose rate may escalate up to 40 ng/kg/min in order to achieve and maintain an age-, size-, and disease-appropriate MAP greater than baseline (above baseline, but less than 90 mmHg, per Investigator discretion). Throughout treatment, LJPC-501 dose rate may be increased to a maximum rate of 40 ng/kg/min, and decreased to a minimum of 1.25 ng/kg/min. Any decision to increase the dose rate above 40 ng/kg/min must be made in consultation with Sponsor. With Sponsor approval, the dose rate may be increased to a maximum of 80 ng/kg/min. Dose administration for more than 24 hours, and for up to 7 days, is permitted with Sponsor consultation.

Duration of treatment:

The target minimum duration of treatment is 24 hours. Continued administration of LJPC-501 for up to 7 days is permitted after consultation with the Sponsor.

Criteria for evaluation: Efficacy:

Primary composite endpoint:

• Proportion of patients with an increase of 25% over Baseline MAP (without an increase in sum NED from baseline) at 2 hours after the initiation of LJPC-501 OR a 25% reduction in sum NED (without a decrease in MAP from baseline) at 2 hours after the initiation of LJPC-501

Secondary endpoints:

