8.3.2. Titration of LJPC-501

LJPC-501 infusion will be started at 5 ng/kg/min. After 5 minutes, the LJPC-501 infusion rate (dose) may be increased to increase MAP and/or allow reduction in SOC vasopressor doses. The dose of LJPC-501 may be increased by 5 ng/kg/min as frequently as every 5 minutes up to a maximum of 40 ng/kg/min. Any decision to increase the dose rate above 40 ng/kg/min must be made in consultation with Sponsor. With Sponsor approval, the dose rate may be increased to > 40 ng/kg/min (to a maximum of 80 ng/kg/min) by increases of 5 to 10 ng/kg/min as frequently as every 5 minutes.

Some patients may be more sensitive to the pressor effects of angiotensin II, and the LJPC-501 dose may be decreased to 1.25 ng/kg/min to avoid hypertension. If MAP exceeds 90 mmHg, SOC vasopressors should be down-titrated first, then LJPC-501 should be down-titrated if MAP remains \geq 90 mmHg.

LJPC-501 treatment should continue for at least 24 hours. Between Hour 2 and Hour 24, LJPC-501 may be titrated between 1.25 and 40 ng/kg/min (or up to 80 ng/kg/min with Sponsor approval). Treatment with LJPC-501 may continue up to 7 days (168 hours) with Sponsor approval.

Changes in LJPC-501 and SOC vasopressor doses should be avoided during MAP measurement at Hour 2 (for evaluation of primary endpoint) and at Hour 24 (for evaluation of secondary endpoint). Interruptions of LJPC-501 administration for longer than 5 minutes before Hour 24 should be avoided, unless required for patient safety, because they may interfere with efficacy assessments. For patients who have received LJPC-501 for the target 24-hour treatment period, treatment may be reinitiated if LJPC-501 treatment has been stopped for 3 hours or less; if treatment has been stopped for more than 3 hours it may not be reinitiated.

33 La Jolla Pharmaceutical Company - Confidential 19 March 2018 (Version 2.0) LJPC-501 infusion should not be stopped abruptly. To discontinue LJPC-501, down titrate by 5 to 20 ng/kg/min every 15 minutes until a dose of 10 ng/kg/min is reached. After 15 minutes at 10 ng/kg/min, down titrate to 5 ng/kg/min. After 15 minutes at 5 ng/kg/min down titrate to 2.5 ng/kg/min. Discontinue the LJPC-501 infusion after 15 minutes at 2.5 ng/kg/min.

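### At ages 2-4 the protocol gives two upper MAP limits for titrating LJPC-501 (80 and 90 mmHg), and its only numeric down-titration instruction uses the higher one

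*Protocol*

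**What the plan says.** The protocol describes the MAP target for LJPC-501 in two ways.

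- **By age.** Section 6.5 allows the dose to be raised or lowered throughout treatment "to achieve an age-, size- and disease-appropriate MAP (Appendix A"). Section 6.2 continues treatment to Hour 24 "with the goal of maintaining age-, size-, and disease-appropriate MAP", again citing Appendix A. Appendix A gives 50-80 mmHg at 2 to 4 years, 60-90 mmHg at 5 to 9 years and 65-90 mmHg at 10 to 17 years.
- **By one ceiling for all ages.** For the first 2 hours, Section 6.2 titrates "to achieve a MAP above baseline, but less than 90 mmHg", and the synopsis methodology says the same. The synopsis dosing paragraph aims for a "MAP greater than baseline (above baseline, but less than 90 mmHg, per Investigator discretion"). Section 6.6 begins from an age-appropriate MAP and then adds the same band: "LJPC-501 dose may be titrated to achieve an age-, size-, and disease-appropriate MAP, which should remain above baseline, but less than 90 mmHg".

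Down-titration has one numeric condition, repeated in the synopsis and in Sections 6.2, 6.6 and 8.3.2: "If MAP exceeds 90 mmHg, SOC vasopressors should be down-titrated first", followed by LJPC-501 if MAP stays at or above 90 mmHg. Section 8.3.2 also permits a lower dose to avoid hypertension, without naming a MAP value.

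Sections 7.1 and 7.2 admit children from 2 years of age, so the youngest Appendix A band is in use.

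**The concern.** The Appendix A ceiling at 2 to 4 years is lower than the ceiling in the titration text and lower than the value at which action is required. Two sites could follow the protocol faithfully and manage the same child differently at, say, 85 mmHg. One would treat the child as above target under Section 6.5. The other would treat the child as within target under the band in the synopsis and Section 6.2.

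This is first a safety matter. Section 4.6 lists transient hypertension as a known risk, names monitoring and appropriate dose titration as the mitigation, and says that the risk of adverse events in children is unknown. In the youngest group the numeric part of that mitigation is not aligned with the protocol's own age range.

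There is also a smaller reporting problem. Without one agreed upper limit, there is no single definition of a MAP excursion in this group to tabulate.

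**Working it through.** The plan states no derived figure on this point, so there is none to reproduce. The check compares the stated limits and then asks whether the gap can be reached.

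**Step 1. Compare ceilings.** Inputs: Appendix A upper limits; the common ceiling and trigger of 90 mmHg (synopsis, Sections 6.2, 6.6 and 8.3.2). Gap = 90 - Appendix A upper limit.

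| Age | Appendix A range (mmHg) | Gap (mmHg) | Whole-number MAP values above the range that do not exceed 90 |
|---|---|---|---|
| 2-4 years | 50-80 | 90 - 80 = 10 | 81 to 90 |
| 5-9 years | 60-90 | 90 - 90 = 0 | none |
| 10-17 years | 65-90 | 90 - 90 = 0 | none |

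The mismatch is confined to the youngest group.

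**Step 2. Apply each instruction to a 2-4 year-old at 81-90 mmHg.**

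- Appendix A, through Sections 6.2 and 6.5: above range.
- Band under 90 mmHg: 81-89 is inside it, provided MAP is above baseline.
- Numeric down-titration instruction: not met at any value from 81 to 90, because MAP must exceed 90.
- Section 6.5 and the hypertension sentence of Section 8.3.2: reduction permitted, with no threshold.

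A value of exactly 90 is awkward at every age. It is not under 90, it does not start the first down-titration step, but it would satisfy the condition for the second.

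**Step 3. Can the Hour 2 goal lead there?** Section 6.2 sets the goal as a 25% rise over Baseline MAP or a 25% fall in sum NED. For the MAP route, the MAP reached is 1.25 × baseline.

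- It reaches 80 mmHg when baseline = 80 / 1.25 = 64 mmHg.
- It reaches 90 mmHg when baseline = 90 / 1.25 = 72 mmHg.

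A 2-4 year-old with a baseline above 64 and below 72 mmHg who meets the MAP goal exactly therefore ends above 80 and below 90 mmHg. That is outside Appendix A but inside the common ceiling. Such baselines lie within 50-80 mmHg, the range to which standard vasopressors are titrated during Screening, so they are compatible with the protocol's own run-in.

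**The case against.** The best reply is that the limits are cumulative. Section 6.6 can be read as an age-appropriate MAP that must also stay above baseline and under 90 mmHg. The target for a 3-year-old would then be at most 80 mmHg, with 90 mmHg as an outer action limit, and a target with a separate action limit is not in itself a contradiction. The target also depends on size and disease at the investigator's discretion, whereas Appendix A is tabulated by age alone, so 81-90 mmHg need not be inappropriate for every child.

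Part of this stands. It shows that reduction at 81-90 mmHg is permitted and arguably implied. It does not remove the inconsistency. The first-2-hours text in the synopsis and Section 6.2 gives the 90 mmHg ceiling without mentioning age, and the synopsis dosing paragraph puts that same band in parentheses after the age-appropriate target. Even on the cumulative reading, the only numeric instruction sits 10 mmHg above the age range, and nothing says that this offset is intended.

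Four stronger readings are tempting, and the protocol does not support them.

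- **That nothing can be done at 81-90 mmHg.** Sections 6.5 and 8.3.2 allow a lower dose, Section 6.2 leaves reduction of standard vasopressors to local protocols and the investigator, and Section 6.6.1 covers clinically significant toxicity. Only a numeric instruction is absent.
- **That the lower limits also contradict each other.** A reader might set the Appendix A lower end against the requirement to stay above baseline. For a 12-year-old with a baseline of 80 mmHg, a MAP above 80 and under 90 lies inside 65-90, so both can be met. Appendix A gives target ranges; it does not state that a patient may be weaned to the bottom of one.
- **That the Hour 24 results are distorted.** A rise in MAP is what titrating a pressor upward is meant to produce, whichever upper limit applies. Change in MAP to 24 hours is a secondary endpoint, and Section 12 plans descriptive reporting.
- **That the ambiguity acts for 168 hours.** That is the optional maximum; the target minimum duration is 24 hours.

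**Conclusion.** The point holds as an internal inconsistency about the upper MAP limit at ages 2 to 4. Its size is 10 mmHg at those ages and nil at 5 to 17 years.

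The comparison of limits rests only on figures in the protocol. The route through the Hour 2 goal assumes a 2-4 year-old with a baseline above 64 and below 72 mmHg who meets the MAP goal by a rise of exactly 25%. The protocol gives no baseline MAP distribution and does not say how many of the 10 to 30 planned patients would be aged 2 to 4, so the number of children affected cannot be estimated.

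The matter is safety-relevant and cheap to correct. It does not bear on the success rule in Table 10, and this check does not say which limit is clinically right.

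**What to change.** The sponsor should reconcile the synopsis, Sections 6.2, 6.5, 6.6 and 8.3.2 and Appendix A, so that the upper MAP limit and the down-titration instruction for ages 2 to 4 are stated consistently, or so that any intended difference between target and action limit is stated explicitly. The wording at exactly 90 mmHg can be tidied in the same edit. The choice of limit and of rule is clinical and belongs to the sponsor.

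For reporting, excursions above the Appendix A range can be tabulated by age group. The schedule already records MAP every 5 minutes for 15 minutes, every 15 minutes to Hour 2, at least hourly thereafter during dosing, and before each titration.

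The cost is amended protocol wording and a note to sites. No new data are needed, and the sample size is unchanged.

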6.6.1. Safety Criteria for Adjustment or Stopping Doses

LJPC-501 administration may continue through Day 7 to support an age- and disease-appropriate MAP. At any time during dosing, if clinically significant toxicities or worsening of symptoms of underlying disease is observed, treatment should be down-titrated and discontinued.

LJPC-501 infusion should not be stopped abruptly (see dose titration guidelines in Section 8.3.2). To discontinue, down titrate by 5 to 20 ng/kg/min every 15 minutes until a dose of 10 ng/kg/min is reached. After 15 minutes at 10 ng/kg/min, down titrate to 5 ng/kg/min. After 15 minutes at 5 ng/kg/min down titrate to 2.5 ng/kg/min. Discontinue LJPC-501 infusion after 15 minutes at 2.5 ng/kg/min.

6.7. Criteria for Study Termination

This study may be prematurely terminated by La Jolla for any reason. Written notification documenting the reason for study termination will be provided to the Investigator by La Jolla.

Circumstances that may warrant termination include, but are not limited to:

- Determination of unexpected, significant, or unacceptable risk to patients
- Unacceptable patient enrollment rate
- Insufficient adherence to protocol requirements
- Insufficient complete and/or evaluable data
- Plans to modify, suspend, or discontinue development of LJPC-501

Table 4:Schedule of Assessments

Assessment	Screening ¹ (-48 to -2 hr)	Baseline	Day 1 0 to 2 hours	Day 1 2 to < 24 hours	Hour 24 (± 1 hr)	Days 2 to 6	EOS ² Day 7 to 10 (± 6 hr)	Day 28 Follow-up (± 2 days)
Informed Consent ³	Х							
Titrate SOC Vasopressors ⁴	Х	Х		X		(X)	(X) ⁵	
Inclusion/Exclusion Criteria	Х							
Demographics	Х							
Medical/Surgical History	Х							
Limited Physical Exam ⁶	Х						Х	
Chest X-ray ⁷	Х							
Hemodynamic Vital Signs (HR, MAP) ⁸	Х	Х	Х	X	Х	Х	Х	
Other Vital Signs (BP, RR, Body Temperature) ⁹	Х	Х	Х		Х	Х	Х	
12-Lead ECG ¹⁰	Х				Х			
Urine Output ¹¹	Х	Х	Х	X	Х	Х	X ⁵	
Fluid Intake ¹²	Х	Х	Х	X	Х	Х	X ⁵	
Tissue Oxygen Saturation ¹³		Х	Х		Х			
Arterial Blood Gas ¹⁴	Х				Х			
Serum Lactate ¹⁵		Х	Х		Х			
Serum Pregnancy Test ¹⁶	Х							
Hematology and Serum Chemistry ¹⁷	Х				Х			
Angiotensin I/II levels 18	Х							
LJPC-501 Administration ¹⁹			Х	X	Х	(X)	(X) ⁵	

Assessment	Screening ¹ (-48 to -2 hr)	Baseline	Day 1 0 to 2 hours	Day 1 2 to < 24 hours	Hour 24 (± 1 hr)	Days 2 to 6	EOS ² Day 7 to 10 (± 6 hr)	Day 28 Follow-up (± 2 days)
PELOD/PRISM/PIM2 Scoring, Including ²⁰ Pupillary Reactions Glasgow Coma Score Diagnosis Ratings	X				Х			
Concomitant Medications and Concomitant Procedures ²¹	X	Х	Х	X	Х	Х	Х	Х
Safety Assessments (AEs/SAEs) ²²			Х	Х	Х	Х	Х	Х

Abbreviations: ABG=arterial blood gas; AE=adverse event; BP=blood pressure; ECG=electrocardiogram; EOS=End of Study; HR=heart rate; MAP=mean arterial pressure; PELOD=Pediatric Logistic Organ Dysfunction; PIM2=Pediatric Index of Mortality 2; PRISM=Pediatric Risk of Mortality; RR=respiratory rate; SAE=serious adverse event; SOC=standard of care.

¹ Screening procedures may be conducted up to 48 hours prior to anticipated initiation of LJPC-501 dosing. SOC procedures collected prior to informed consent may be used to qualify patients for the study.

² Patients will be followed for a minimum of 7 days, or for 72 hours (3 days) ± 6 hours following discontinuation of LJPC-501, whichever is later, before end of study (EOS) assessments are completed. Depending on the duration of treatment, EOS may occur on Day 7 through Day 10. If a patient is treated for the target minimum of 24 hours, EOS will occur on Day 7.

³ Informed consent must be obtained before any study related activities can occur. SOC procedures conducted prior to informed consent may be used to qualify patients for the study, if performed within the specified time window for the procedure (Section 8.5).

⁴ All patients will have their SOC vasopressors titrated (to a total sum NE equivalent dose of > 0.1 μg/kg/min to be eligible) for a minimum of 2 hours but not for longer than 48 hours prior to initiation of LJPC-501 dosing. During the first two hours of LJPC-501 treatment, SOC vasopressor dosing may be decreased, but not increased, unless adjustment is required for safety reasons. After Hour 2 and throughout LJPC-501 treatment, up to Day 7, titration of SOC vasopressors may continue with the goal of sparing the use of catecholamines. (X) indicates time periods during which LJPC-501 dose administration is optional. During treatment with LJPC-501, SOC vasopressor titration should be tracked.

⁵ Do not continue administration for more than 7 days (168 hours).

⁶ A limited physical exam (PE) focused on extremities, abdominal region and neurological system should be performed at Screening and at EOS. Screening PE will also document body weight and height.

⁷ Chest X-ray is optional. SOC chest X-rays collected prior to informed consent but within 24 hours prior to LJPC-501 treatment initiation may be used.

⁸ Patients will be continuously monitored during the first 24 hours following initiation of LJPC-501. Hemodynamic vital signs, (MAP, HR) must be documented hourly during Screening for a minimum of 2 hourly readings within 24 hours prior to LJPC-501 treatment initiation. The average of the 2 MAP readings will determine the Screening MAP. MAP must be measured during Baseline at approximately -15 min, -5 min, and 0 min (or just prior to initiation of LJPC-501). The average of these 3 MAP values will determine the Baseline MAP. MAP and HR will be recorded on Day 1 prior to every dose titration and minimally every 5 minutes during the first 15 minutes, every 15 minutes during the first 2 hours, and hourly thereafter through the duration of LJPC-501 administration (target minimum of 24 hours). If a patient remains on LJPC-501 beyond 24 hours, documentation of MAP and HR should continue as during Hours 2 to 24 (ie, just prior to any dose adjustment and a minimum of hourly through discontinuation of LJPC-501.) After LJPC-501 treatment, but before EOS, documentation of MAP and HR should occur once daily.

1

Clinical Protocol

- ⁹Other vital signs should be assessed at Screening, just prior to initiation of dosing on Day 1, on Day 1 at Hour 2, at Hour 24, and once daily on Days 2-7. ¹⁰ ECG assessments will be performed at Screening and at Hour 24 after initiation of LJPC-501, if possible.
- ¹¹ Urine output will be measured and recorded as appropriate for the patient's age, per local SOC, if possible. Assessments for the 24 hours prior to LJPC-501 administration will be recorded, if available. Urine output will be measured and recorded continuously through Day 7.
- ¹² IV fluid intake will be assessed for the 24-hour period prior to LJPC-501 administration, if available. IV fluid intake will be measured and recorded continuously through Day 7 per local practice.
- ¹³ Tissue oxygen saturation will be measured non-invasively, if possible, at baseline, Hour 2, and Hour 24.
- ¹⁴ An ABG sample will be collected during Screening (within 6 hours prior to LJPC-501 administration) and at Hour 24.
- ¹⁵ Serum lactate (arterial or venous) will be collected at baseline, Hour 2, and Hour 24. Any measurements taken at other times will also be recorded in the electronic case report form (eCRF).
- ¹⁶ Serum pregnancy tests are required for female patients of childbearing potential.
- ¹⁷ Blood for clinical chemistry and hematology testing will be collected at Screening (within 6 hours prior to LJPC-501 administration), and at Hour 24 (Section 11.1.8).
- ¹⁸ If total blood collection volume limits (per institutional guidelines) allow, blood samples will be collected for angiotensin I/II levels.
- ¹⁹ See Section 6.2 and Section 6.6 for study periods and dose adjustment guidelines. (X) indicates time periods during which dose administration is optional.
- ²⁰ All parameters of the PELOD/PRISM/PIM2 scores should be performed at Screening and at Hour 24. The Screening PELOD/PRISM/PIM2 scores must be determined with data obtained no more than 6 hours prior to initiation of LJPC-501 dosing. See Appendix C, Appendix D, and Appendix E.
- ²¹ Record all concomitant medications (including vasopressors) and any procedures performed through Day 28. In addition, record all vasopressors administered up to 2 days prior to beginning LJPC-501 administration. Total daily dose for each vasopressor administered through Day 28 may be recorded after completion of LJPC-501 administration.
- ²² Safety will be evaluated at every time point. On Day 28, a phone call follow-up to the patient's parent(s) or legal guardian(s), the patient's primary care physician, and/or a chart review will be conducted to determine if reportable safety events occurred between EOS and Day 28.

